4.7.2. Dosing for azacitidine and decitabine-related toxicities

Patients with drug-related toxicities that are manageable with supportive therapy may not require dose reductions. For patients with other drug-related toxicities, the following dose adjustment rules apply:

NCI CTCAE Grade	Action
Grade 0-2 non-hematological toxicity	No dose reduction. Grade 2 toxicities that are persistent and intolerable (e.g. stomatitis) can result in dose delays or dose reductions to the next lower dose level in Cycle 2 or beyond.

Grade 3-4 clinically significant non-hematological toxicity	Hold until recover to NCI CTCAE grade 0-1 If recovery occurs within 2 weeks after treatment has been held, dose should be reduced to –1 dose level, if applicable.
---	---

Standard dose reductions for azacitidine and decitabine are described in the following table (please note patients should start at the dose level they were receiving prior to study enrollment):

Dose level	Decitabine (in mg/m ² for 5 days)	Azacitidine (in mg/m ² for 7 days)
0	20	75
-1	15	50
-2	10	25
-3	10 for 4 days	25 for 5 days

Patients with delayed recovery of neutrophils to $1 \times 10^9/L$ and/or platelets to $75 \times 10^9/L$ in the absence of residual disease may have dose reductions by 1 dose level in subsequent cycles.

Patients with serious infectious complications in prior cycles may have the subsequent cycles administered at one dose level reduction in subsequent cycles.

Dose reductions or delays different than those described above are acceptable after discussion with the sponsor and the PI, and will require documentation of the rationale for such action.

4.7.3. For patients with adverse events that are due to one of the two agents, dose adjustments to only one of the study drugs may be adjusted as per the guidelines mentioned above.

4.7.4. For patients on Arm B, discontinuation of the hypomethylating agent and continued therapy with eltrombopag monotherapy after cycle 2 may be considered at the discretion of the investigator.

5. STUDY PROCEDURES

5.1 Screening (Visit 1)

The following procedures are performed during screening, staging and workup (see also Table 5.3). These procedures are to be performed within 4 weeks prior to study drug administration, except where indicated.

A signed and dated IEC/IRB approved informed consent form must be obtained before any study specific procedures are performed. Procedures that are part of routine care are not considered study specific procedures. All subjects will be screened for eligibility before enrollment. Once the subject has met all inclusion criteria, they will be enrolled onto the study.

Table 5.1: Procedures during Screening, Staging and Workup

Procedures	Specifics
Informed consent	
Full History and Physical Examination	
History – present illness, prior surgeries, other medical illnesses, review of systems, allergies, prior therapy for cancer and concurrent meds;
 
Physical exam – record weight, and note abnormalities in any major organ system (including but not limited to neurologic, head and neck, lymph nodes, cardiovascular, pulmonary, abdomen, extremities), note and measure sites of disease

Concomitant Medications	
Vital signs (including temperature, pulse, and blood pressure)	
ECOG performance status	
Urine or blood pregnancy test (females of child-bearing potential only)	Within 7 days prior to first dose

Disease status (IPSS classification and WHO disease classification)
 
Note: Bone marrow biopsy or aspirate within 4 weeks prior to first dose of drug in all patients. Cytogenetics and immunohistochemistries performed as indicated.
	
Staging with bone marrow biopsy and/or aspirates for disease assessment.

Serum chemistries (repeat if screening chemistries completed greater than 72 hours prior to the first dose).	
Sodium, potassium, blood urea nitrogen, creatinine, glucose, calcium, phosphate, magnesium, AST and/or ALT, total bilirubin, alkaline phosphatase, and uric acid.
 
Note that serum iron, transferrin, transferrin saturation, total iron binding capacity and ferritin only need to be performed once and do not need to be repeated.

CBC with differential (repeat if screening test completed greater than 72 hours prior	Differential may be omitted if WBC $\leq 0.5 \times 10^9/L$

to the first dose)	
--------------------	--

5.2 Treatment Assignment

This is a two arm, non randomized study. Selection of treatment arm will be performed by the patient and the treating physician in the best interest of the patient, based upon available space in either Arm.

5.3 On-Study Procedures

Table 5.3: Study Calendar

PROCEDURES	Pre-Study Screen ^o	Cycle 1 Day 1	Cycle 1 Day 8 (+/- 2 days)	Cycle 1 Day 15 (+/- 2 days)	Cycle 1 Day 22 (+/- 2 days)	Day 1 Cycle 2 onwards (+/- 7 days)	End of Treatment Visit (+/- 7 days)	Safety Visit 28 days after last dose (+/- 28 days)
Informed Consent	X							
Eligibility	X	X						
Medical History	X							
Vital Signs	X	X	X	X	X	X	X	X
Physical Exam and Performance Status	X	X				X	X	X
Concomitant Medications	X	X	X	X	X	X	X	X
Transfusion and Supportive Care Assessment	X					X	X	X
CBC with differential	X*	X	X	X	X	X ¹	X	X ²
Blood Chemistries (AST, ALT, bilirubin)	X ^{^A}	X	X	X	X	X ¹	X	X
Bone marrow aspiration and/or biopsy	X					X ³	X	
IPSS score & WHO disease classification	X						X	
Pregnancy Test	X†							
Investigational Drug Dispense		X				X		
AE and SAE assessment	X	X	X	X	X	X	X	X
Optional: Correlative Studies	X							

^oScreening must be performed within 4 weeks prior to study drug initiation / study start unless otherwise indicated

*CBC with differential and blood chemistries including iron studies (sodium, potassium, BUN, creatinine, glucose, calcium, phosphate, magnesium, AST, ALT, total bilirubin, alkaline phosphate, uric acid, serum iron, transferrin, , total iron binding capacity and ferritin) must be performed within 72 hours of Cycle 1 Day 1

[^]Serum iron, transferrin, total iron binding capacity and ferritin are required only on Cycle 1 Day 1 and do not need to be repeated

†Within 7 days of Day 1 in females of child-bearing potential

¹Weekly CBC with differential and blood chemistries required until stable counts, and bi-weekly x4 weeks after any change in eltrombopag dosing

²Weekly CBC with differential should be performed weekly for the 4 weeks after discontinuation of eltrombopag

³Bone marrow aspiration and biopsy with cytogenetics required for study entry, at completion of cycle 2, and then every 3 cycles as clinically indicated. Cytogenetics do not need to be repeated if normal at study start.

⁴Optional correlative studies will be performed on bone marrow sample taken at screening. The studies will include an analysis of mutational status of 53 genes known to be affected in acute leukemias as well as gene expression profiling, and evaluation of any potential relationship with the presence or absence of mutations and response will be assessed.

5.4. End of Study Visit:

Subjects will undergo an End of Treatment Visit at the time of discontinuation of investigational product. A bone marrow biopsy and/or aspirate with cytogenetics for IPSS and WHO classification will be performed at this visit. Cytogenetics can be omitted if normal at study start.

5.5. Safety Visit:

Whenever possible, subjects will undergo an End of Study Safety Visit 4 weeks after his/her last dose of investigational product in the treatment period.

5.6. Criteria for Removal from Study:

Treatment is expected to continue until one of the following criteria applies:

- Lack of objective response after 2 cycles of therapy unless eltrombopag is considered to be of clinical benefit to the patient
- Unacceptable adverse event(s)
- Discontinuation of study drug for more than 6 weeks
- Clinically significant progressive disease
- Possibility of undergoing allogeneic stem cell transplantation
- Intercurrent illness that prevents further administration of treatment
- Patient request
- General or specific changes in the patient's condition that renders the patient unacceptable for further treatment in the judgment of the investigator

Continuation of therapy beyond 12 months will be considered on a case-by-case basis for patients deriving clinical benefit after discussion with the PI and sponsor.

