Prognosis in HMA-failure patients is extremely poor. Jabbour et al⁹ report a median survival of merely 4 months in MDS patients with progressive disease after decitabine (Figure 1), and Prebet et al⁷ identified a similar median survival of 5.6 months in MDS patients with progressive disease after 5-azacytidine. There are no currently approved agents in the setting of HMA-failure MDS patients, and there are limited therapeutic options, particularly given the increased age and frequent comorbidities of this population.

As alluded to above, the platelet count in MDS patients is critically important, and impacts both treatment decisions and overall survival in the majority of MDS patients. Among 2410 patients with MDS referred to the MD Anderson Cancer Center, 67% had a platelet count $<100 \times 10^9/L$ at the time of their initial consultation, and even within the lower-risk MDS categories, over 10% of patients experience life-threatening thrombocytopenia ($<20 \times 10^9/L$) at presentation.¹⁰ Thrombocytopenia has been identified as an independent and adverse prognostic factor for overall survival in MDS at all stages.¹¹ An analysis of 892 primary MDS subjects identified a median survival in patients with platelet counts $< 100 \times 10^9/L$ of 27 months, compared to 60 months for patients with platelet counts $\geq 100 \times 10^9/L$.¹² Furthermore, the mainstay of treatment for thrombocytopenia in MDS patients, transfusions, are short-lived, and associated with transfusion reactions, allo-immunization, transmission of bacterial and viral infections, and have no impact on the underlying disease biology.

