6. RESPONSE DEFINITIONS

6.1. Patients' overall response will be assessed after at least 2 cycles of treatment but no more than after 6 cycles, and each cycle is 28 days.

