6.2.3. Secondary Efficacy Endpoints

The key secondary endpoints for this study are:

- The incidence of transformation to AML by FAB during treatment period and follow-up
- The incidence and severity of bone marrow fibrosis during treatment period and follow-up
- Proportion of patients achieving a platelet response during treatment; and proportion of patients achieving a durable platelet response.
 - o Platelet IWG-2006: A complete response is defined as a platelet count $> 100 \times 10^9/L$; and a major response defined as an increase of platelet count by higher than $30 \times 10^9/L$.
 - o Durable platelet count: in which a hematologic improvement in platelets (HI-P) defined as either an increase $\geq 30 \times 10^9/L$ from patients with a baseline platelet count $\geq 20 \times 10^9/L$, or an increase from $< 20 \times 10^9/L$ to $\geq 20 \times 10^9/L$ and by at least 100%, present for ≥ 8 weeks.

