8.4.2. Analysis of Key Study Endpoints

The primary endpoint is overall response rate (ORR). The ORR in each arm will be evaluated along with the exact 95% confidence interval. Given the limited sample size, no formal comparison will be made between these two arms in terms of ORR.

Secondary endpoints include platelet response, durable platelet response, transformation to AML, incidence of bone marrow fibrosis, and time-to-event outcomes such as progression-free survival (PFS) and overall survival (OS). The probabilities of PFS and OS will be estimated using the method of Kaplan and Meier. The incidence rates of other binary secondary endpoints will be estimated, along with the exact 95% confidence intervals. Subjects that discontinue the study prior to having achieved a clinical response will be considered to have not had an event.

Patients receiving growth factors other than eltrombopag (erythropoietin, GM-CSF or G-CSF) will not be considered in the HI analysis for the time periods specified in Section 4.5.3 Supportive Care Guidelines. Hemoglobin levels and platelet counts collected from patients that have received a transfusion within the last 3 days will not be considered in the analysis.

Survival or times to failure and time to progression functions will be estimated using the Kaplan-Meier method. The two-sided log-rank test will be used to assess the differences of time to events between groups.

The total number of dose administrations, the average dose (mg), and the cumulative dose administered will be summarized by eltrombopag treatment group.

Blood chemistry and complete blood counts will be summarized by treatment group at each time point.

Additional exploratory analyses of the key study endpoints will be performed as deemed appropriate.

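### Scheduled observation ends 28 days after the last dose, yet OS, PFS and AML transformation are analysed; if the calendar is followed, OS would probably be overestimated and later AML missed

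*Combined protocol and SAP*

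**What the plan says.** **Calendar.** Table 5.3 (section 5.3) has no column after "Safety Visit 28 days after last dose (+/- 28 days)". Section 5.5 makes this the end-of-study visit and conditional: "Whenever possible, subjects will undergo an End of Study Safety Visit 4 weeks after his/her last dose".

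**When non-responders stop.** Section 5.6, on removal from study, lists "Lack of objective response after 2 cycles of therapy unless eltrombopag is considered to be of clinical benefit to the patient". Section 6.1 states that "each cycle is 28 days". Patients with benefit may stay for 12 cycles or longer (sections 4.1.4 and 4.2.2).

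**Deaths reported as SAEs.** Section 6.2.2.1 captures SAEs until 30 days after the last dose, and later ones only if related to study treatment.

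**Analysis.** Section 8.4.2 counts among the secondary endpoints "time-to-event outcomes such as progression-free survival (PFS) and overall survival (OS)" and says "The probabilities of PFS and OS will be estimated using the method of Kaplan and Meier". It adds a two-sided log-rank test between groups. It also treats subjects who discontinue before a clinical response as event-free, without saying for which endpoints.

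**AML.** Section 6.2.3 lists "The incidence of transformation to AML by FAB during treatment period and follow-up". Section 8.4.2 analyses it as a binary incidence with an exact confidence interval.

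**Not stated anywhere.** The documents give no contact interval or duration for post-treatment follow-up, no data cut-off, and no censoring date for OS or PFS. Section 6.2.1 names the survival events only.

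**The concern.** The planned analyses need information that the planned visits do not collect. Treatment, and with it scheduled contact, ends early mainly for patients who have not responded. Kaplan-Meier assumes that patients who leave observation have the same subsequent risk as those who remain. If non-responders drop out of view at the safety visit and their risk of death is higher, the later part of the OS curve rests increasingly on responders and lies too high. The log-rank comparison would use the same incomplete data. AML that develops after exit would not be counted, although the patient stays in the denominator. Contacts that were never made are hard to recover at the analysis stage, so this goes beyond a missing detail in the analysis text.

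**Working it through.** The documents give no follow-up length, event count or censoring date for these endpoints, so there is no stated figure to reproduce.

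**Step 1: nominal last contact of a non-responder.** 2 cycles × 28 days + 28 days = 84 days = 12 weeks. With the window of ±28 days this is 56 to 112 days, or 8 to 16 weeks.

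**Step 2: non-responders alive at that visit.** Section 2.1 gives "a median survival of merely 4 months in MDS patients with progressive disease after decitabine" and 5.6 months after azacitidine. With exponential survival, S_nr(t) = exp(−ln 2 × t / median), and 84 days = 2.76 months:
- median 4 months: 62% alive at week 12 (73% at week 8, 53% at week 16);
- median 5.6 months: 71% alive at week 12 (80% at week 8, 63% at week 16).

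Most non-responder deaths would therefore fall after the last scheduled contact.

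**Step 3: large-sample effect on OS if all non-responders are censored at c = 2.76 months.** Let f be the responder share: 18% in Arm A and 25% in Arm B (the target ORRs in section 8.2.1).
- True curve: S(t) = f·S_r(t) + (1−f)·S_nr(t).
- Kaplan-Meier limit for t > c: S(c) × S_r(t)/S_r(c).

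Responder survival is not in the documents. Medians of 9, 12 and 18 months are assumed, which imply responder-to-non-responder hazard ratios from 4/18 = 0.22 to 5.6/9 = 0.62.

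Example with f = 0.18 and medians of 4 and 12 months:
- True 12-month OS = 0.18 × 0.500 + 0.82 × 0.125 = 0.19.
- S(c) = 0.18 × 0.853 + 0.82 × 0.620 = 0.662.
- Kaplan-Meier limit = 0.662 × 0.500/0.853 = 0.39.

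Over all 12 combinations the overstatement is 5.8 to 15.9 points at 6 months and 9.2 to 25.4 points at 12 months.

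**Step 4: weaker association between response and survival.** This uses the same model with the hazard ratio set directly.

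| Hazard ratio | Bias at 26 weeks | Bias at 52 weeks |
|---|---|---|
| 1 | 0 | 0 |
| 0.75 | about 4 points | about 5 to 6 points |
| 0.33 | up to about 13 points | up to about 21 points |

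**Step 5: some non-responders stay on for clinical benefit.** Let a share s of them stay under observation with the same hazard as other non-responders. The limit becomes S(c) × [f·S_r(t) + (1−f)·s·S_nr(t)] / [f·S_r(c) + (1−f)·s·S_nr(c)]. With s = 25% (assumed), the 12-month overstatement over the 12 combinations of step 3 falls to about 4 to 12 points. For f = 0.18 and medians of 4 and 9 months it falls from 14.7 to 5.9 points, and to 2.7 with s = 50%.

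**Step 6: precision.** With a hazard ratio of 0.5 and s = 0, about 3 of 23 patients in Arm A and 5 of 23 in Arm B remain at risk just after week 12, against 15 to 17 with full follow-up. With equal hazards there is no bias, but a similar loss of patients at risk.

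**The case against.** The strongest reply is that no written rule censors anyone at week 12. Table 5.3 lists on-study procedures, all patients come from one centre, vital status can be taken from charts without a calendar row, and the documents name a follow-up period for AML and fibrosis. This stands to the extent that censoring at the safety visit follows from the calendar and is not a stated rule. It does not close the gap, because nothing in the plan obliges anyone to collect the data or fixes a cut-off.

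A reader might infer that after three months the curves describe responders only. The documents do not support that: section 5.6 lets non-responders continue for clinical benefit, and section 6.1 allows response assessment up to 6 cycles.

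The size is also open to challenge. Responder medians of 9-18 months are assumptions. The medians of 4 and 5.6 months describe patients with progressive disease, whereas section 3.1 also admits patients with persistent cytopenias only and patients with Low or intermediate-1 IPSS risk. Both points stand, so the range illustrates what could happen and does not predict this trial's bias.

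A reader might also carry the OS figures over to PFS and AML. For PFS, patients who leave because of progression already have their event. AML is a binary incidence, so the Kaplan-Meier argument does not apply, and the end-of-treatment marrow (section 5.4) captures AML present at exit.

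Finally, OS and PFS are absent from the objectives in section 1.2 and from the key secondary endpoints in section 6.2.3, and the arms are not randomised. That limits the importance of the point but does not remove it, since section 8.4.2 still plans to report both.

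**Conclusion.** The gap is real and should be closed. The plan ends scheduled observation at the safety visit and SAE capture at 30 days, then analyses outcomes that mostly occur later. If the calendar is followed, OS would probably be overestimated. The bias is zero with equal hazards. It reaches about 16 points at 6 months and 25 points at 12 months under exponential survival, responder medians of 9-18 months, and censoring of every non-responder at week 12. Continuation for clinical benefit reduces it. PFS is affected only for patients who leave without progression; its bias was not calculated. AML arising after exit would be missing from the incidence, and more so if the no-event sentence in 8.4.2 were applied to AML. It would go too far to say that non-responders are censored at 12 weeks or that the curves are certainly biased: the documents establish neither. The ORR decision under the two-stage designs in section 8.2.1 is not affected.

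**What to change.** 1. Add a post-treatment row to Table 5.3: vital status, progression and AML status, and subsequent therapy, by telephone or chart review every 3 months until death or one common data cut-off, for every patient whatever the reason for leaving treatment.
2. In section 8.4.2, censor OS at the date last known alive or at the cut-off.
3. In the same section, state that the sentence counting early discontinuations as event-free applies to response endpoints only.

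The cost is a small amount of telephone or chart work for at most 46 patients at one centre, with no added procedures.

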6. RESPONSE DEFINITIONS

6.1. Patients' overall response will be assessed after at least 2 cycles of treatment but no more than after 6 cycles, and each cycle is 28 days.

6.2. Study Endpoints

6.2.1. Primary Efficacy Endpoint: The overall response rate (CR + PR + HI) based on the IWG-2006 criteria. Responses must last at least 4 weeks.

Complete Remission:

- Bone marrow: $\leq 5\%$ myeloblasts with normal maturation of all cell lines
- Persistent dysplasia will be noted
- Peripheral blood
 - o Hemoglobin $\geq 11\text{g/dL}$
 - o Platelets $\geq 100 \times 10^9/\text{L}$
 - o Neutrophils $\geq 1.0 \times 10^9/\text{L}$
 - o Blasts 0%

Partial Remission:

- All CR criteria if abnormal before treatment except:
 - o Bone marrow blasts decreased by $\geq 50\%$ over pretreatment but still $> 5\%$

Stable Disease:

- Failure to achieve at least PR, but no evidence of progression for >8 weeks

Failure:

- Death during treatment or disease progression characterized by worsening of cytopenias or significant increase in percentage of bone marrow blasts

Hematologic Improvement (HI) Response Criteria*: responses must last at least 8 weeks

- **Erythroid response** (if pretreatment hemoglobin $< 11\text{g/dL}$)
 - o Hemoglobin increase by $\geq 1.5\text{g/dL}$
 - o Relevant reduction of units of RBC transfusions by an absolute number of at least 4 RBC transfusions/8 wk compared with the pretreatment transfusion number in the previous 8 wks. Only RBC transfusions given

for a Hgb of ≤ 9.0 g/dL pretreatment will count in the RBC transfusion response evaluation

- **Platelet response** (if pretreatment platelets $< 100 \times 10^9/L$)
 - o Absolute increase of $\geq 30 \times 10^9/L$ for patients starting with $> 20 \times 10^9/L$ platelets
 - o Increase from $< 20 \times 10^9/L$ to $> 20 \times 10^9/L$ and by at least 100%
- **Neutrophil response** (if pretreatment $< 1.0 \times 10^9/L$)
 - o At least 100% increase and an absolute increase of $> 0.5 \times 10^9/L$

*Pretreatment counts averages of at least 2 measurements (not influenced by transfusions) for at least one week

Progression or relapse after HI‡:

- At least 1 of the following:
 - o At least 50% decrement from maximum response levels in granulocytes or platelets
 - o Reduction in hemoglobin by ≥ 1.5 g/dL
 - o Transfusion dependence
- ‡In the absence of another explanation, such as acute infection, repeated courses of chemotherapy (modification), gastrointestinal bleeding, hemolysis, and so forth. It is recommended that the 2 kinds of erythroid and platelet responses be reported overall as well as by the individual response pattern.

Relapse after CR or PR:

- At least 1 of the following
 - o Return to pretreatment bone marrow blast percentage
 - o Decrement of $\geq 50\%$ from maximum remission/response levels in granulocytes or platelets
 - o Reduction in hemoglobin concentration by ≥ 1.5 g/dL or transfusion dependence

Cytogenetic Response:

- Complete: Disappearance of the known chromosomal abnormality without appearance of new abnormalities
- Partial: At least 50% reduction of the chromosomal abnormality in 20 metaphases

Disease Progression:

For patients with:

- Less than 5% blasts: $\geq 50\%$ increase in blasts to $> 5\%$ blasts
- 5-10% blasts: $\geq 50\%$ increase to $> 10\%$ blasts
- 10-20% blasts: $\geq 50\%$ increase to $> 20\%$ blasts
- 20-30% blasts: $\geq 50\%$ increase to $> 30\%$ blasts

Any of the following:

- At least 50% decrement from maximum remission/response in granulocytes or platelets
- Reduction in hemoglobin by ≥ 2 g/dL
- Transfusion dependence

Survival Endpoints:

- Overall: death from any cause
- Event free: failure or death from any cause
- PFS: disease progression or death from MDS
- DFS: time to relapse
- Cause specific death: death related to MDS

